7.2.2.2.1. Insulin Glargine Dose Titration Algorithm

The decision to adjust insulin glargine doses will be based upon the median of the last 3 daily FBG (SMBG) values (preferably most recent readings) collected after the previous dose assessment. If fewer than 3 values are available for assessment, then the average value will be calculated and used to adjust the dose. If the median or average FBG value is within the target FBG range, then there will be no resulting change in dose. If that value is ≥ 5.6 mmol/L, the dose will be increased based on the titration algorithm provided in [Table GBGO.4](#) (Davies et al. 2005). In the case of recorded hypoglycemic episodes any time during the period included in the assessment, the criteria provided in [Table GBGO.4](#) should be followed.

Table GBGO.4. Insulin Glargine Treatment-to-Target Algorithm

Median or Average BG Before Breakfast (for Titration of Evening Dose)	Increase in Basal Dose (Units)
<70 mg/dL (<3.9 mmol/L)	Decrease to previous lower dose*
70-<100 mg/dL (3.9-5.6 mmol/L)	No adjustment
100-<120 mg/dL (5.6-6.7 mmol/L)	+1 to +2 U [#]
120-<140 mg/dL (6.7-7.8 mmol/L)	+ 2 U
140-<180 mg/dL (7.8-10.0 mmol/L)	+ 4 U
≥180 mg/dL (>10.0 mmol/L)	+6 to +8 U [#]

* The patient will be administered with the previous lower dose if he/she has documented hypoglycemia or probable symptomatic hypoglycemia.

[#] Insulin glargine dose adjustment will be discussed with the patient and determined by the investigator before Week 8 as preparation and training for implementation of the patient self-titration according to the treatment-to-target algorithm after Week 8 (Section 5.1).

Abbreviations: BG = blood glucose; U = unit(s).

7.3. Blinding

This is a double-blind study. To preserve the blinding of the study, a minimum number of Lilly personnel will see the randomization table and treatment assignments before the study is complete.

Emergency unblinding for AEs may be performed through the IWRS, which may supplement or take the place of emergency codes generated by a computer drug-labeling system. This option may be used ONLY if the patient's well-being requires knowledge of the patient's treatment assignment. All calls resulting in an unblinding event are recorded and reported by the IWRS.

In case of an emergency, the investigator has the sole responsibility for determining if unblinding of a patient's treatment assignment is warranted for medical management of the event. The Patient safety must always be the first consideration in making such a determination. If a patient's treatment assignment is unblinded, Lilly must be notified immediately. If the investigator decides that unblinding is warranted, it is the responsibility of the investigator to promptly document the decision and rationale and notify Lilly as soon as possible.

If an investigator, site personnel performing assessments, or patient is unblinded, the patient must be discontinued from the study. In cases where there are ethical reasons to have the patient remain in the study, the investigator must obtain specific approval from a Lilly clinical research physician (CRP) for the patient to continue in the study.

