Patients are required to continue using their concomitant OAMs throughout the treatment period. Discontinuation of these medications or dose changes are not permitted, except in certain situations (see Sections 7.7.1 and 7.7.5.2 for details).

Patients will be permitted to use concomitant medications that they require during the study, except certain medications that may interfere with the assessment of efficacy and safety characteristics of the study treatments (Section 7.7).

Patients who develop severe, persistent hyperglycemia based on prespecified thresholds (see Sections 7.7.5.3 and 9.2.2.1) will receive a new glucose-lowering intervention (“rescue therapy”) and will also continue with study drug. Patients who need hyperglycemic rescue therapy will continue in the trial until they complete all study visits. Patients who permanently discontinue study drug prior to the Safety Follow-Up Period will also be required to continue in the trial and should receive a new glucose-lowering intervention (Section 7.7.1).

Study governance considerations are described in detail in [Appendix 3](#).

Stabilization Period (End of Visit 3 to Visit 6 [Weeks 0 to 4])

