8.1. Discontinuation from Study Treatment

8.1.1. Permanent Discontinuation from Study Treatment

Possible reasons leading to permanent discontinuation of investigational product:

- **Patient Decision**
 - The patient requests to discontinue investigational product.
- **Discontinuation due to a hepatic event or liver test abnormality.** Patients who are discontinued from investigational product due to a hepatic event or liver test abnormality should have additional hepatic safety data collected via the electronic case report form (eCRF).

Discontinuation of the investigational product for abnormal liver tests **should be** considered by the investigator when a patient meets one of the following conditions after consultation with the Lilly designated medical monitor:

- Alanine aminotransferase (ALT) or aspartate aminotransferase (AST) $>8X$ upper limit of normal (ULN)
- ALT or AST $>5X$ ULN for more than 2 weeks
- ALT or AST $>3X$ ULN and total bilirubin level (TBL) $>2X$ ULN or prothrombin time $>1.5X$ ULN
- ALT or AST $>3X$ ULN with the appearance of fatigue, nausea, vomiting, right upper-quadrant pain or tenderness, fever, rash, and/or eosinophilia ($>5\%$)
- Alkaline phosphatase (ALP) $>3X$ ULN
- ALP $>2.5X$ ULN and TBL $>2X$ ULN
- ALP $>2.5X$ ULN with the appearance of fatigue, nausea, vomiting, right quadrant pain or tenderness, fever, rash, and/or eosinophilia ($>5\%$)

In addition, patients will be discontinued from the investigational product in the following circumstances:

- If a patient is inadvertently enrolled and it is determined that continued treatment with study drugs would not be medically appropriate;
- Acute or chronic pancreatitis;
- If a patient is diagnosed with an active or untreated malignancy (other than basal or squamous cell skin cancer, in situ carcinomas of the cervix, or in situ prostate cancer) after randomization;

- If a patient is diagnosed with C-cell hyperplasia or medullary thyroid carcinoma (MTC) after randomization;
- Any other TEAE, SAE, or clinically significant laboratory value for which the investigator believes that permanent study drug discontinuation is the appropriate measure to be taken;
- Any significant study drug-related hypersensitivity reaction;
- If a non-study GLP-1 receptor agonist is initiated, and the patient refuses to discontinue this medication;
- If female patient becomes pregnant;
- If a patient is diagnosed with T1D;

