- If an investigator, site personnel performing assessments, or patient is unblinded;
- If the investigator or sponsor decides that the patient should be withdrawn from study drug; if the investigator decides to permanently discontinue study treatment because of an SAE or a clinically significant laboratory value, Lilly or its designee should be alerted immediately.
- if the patient or the patient's designee, for example, legal guardian, requests that the patient be withdrawn from study drug

Patients who stop the study drug permanently will receive another glucose-lowering intervention (Section 7.7.1) and will continue participating in the trial according to the protocol to collect all planned efficacy and safety measurements.

Patients discontinuing from the investigational product prematurely for any reason should complete AE and other follow-up procedures per Section 2 Schedule of Activities, Section 9.2 Adverse Event, and Section 9.4 Safety of this protocol.

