9.2.2.3. Pancreatitis

Acute pancreatitis is defined as an AE of interest in all trials with dulaglutide, including this trial. Acute pancreatitis is an acute inflammatory process of the pancreas that may also involve peripancreatic tissues and/or remote organ systems (Banks and Freeman 2006). The diagnosis of acute pancreatitis requires 2 of the following 3 features:

- abdominal pain, characteristic of acute pancreatitis (generally located in the epigastrium and radiates to the back in approximately half the cases [Banks and Freeman 2006; Koizumi et al. 2006]; the pain is often associated with nausea and vomiting);
- serum amylase (total and pancreatic) and/or lipase $\geq 3 \times \text{ULN}$;
- characteristic findings of acute pancreatitis on computed tomography (CT); scan or magnetic resonance imaging (MRI).

If acute pancreatitis is suspected, appropriate laboratory tests (including levels of pancreatic amylase and lipase) should be obtained via the central laboratory (and locally, if needed).

Imaging studies, such as abdominal CT scan with or without contrast, MRI, or gallbladder ultrasound, should be performed. If laboratory values and/or abdominal imaging support the diagnosis of acute pancreatitis, the patient must discontinue therapy with investigational product, but will still continue in the study on another glucose-lowering regimen (see Section 7.7.1 and Section 8.1.1 for details on the introduction of new antihyperglycemic interventions).

The most appropriate diabetes therapeutic regimen will be decided by the investigator, based on

the patient's clinical status. A review of the patient's concomitant medications should be conducted to assess any potential causal relationship with pancreatitis.

Each case of AE of pancreatitis must be reported. If typical signs and/or symptoms of pancreatitis are present and confirmed by laboratory values (lipase or amylase [total and/or pancreatic]) and imaging studies, the event must be reported as an SAE. For a potential case that does not meet all of these criteria, it is up to the investigator to determine the seriousness of the case (AE or SAE) and the relatedness of the event to study drug.

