9.2.2.6. Allergic/Hypersensitivity Reactions

All allergic or hypersensitivity reactions will be reported by the investigator as either AEs or, if any serious criterion is met, as SAEs. Additional data, such as type of reaction and treatment received, will be collected on the eCRF for any AEs or SAEs deemed related to study drug by the investigator. Injection site reactions will be collected on an eCRF separate from the hypersensitivity reaction eCRF. Study drug should be temporarily interrupted in any individual suspected of having a severe or serious allergic reaction to study drug (Section 8.1.2). Study drug may be restarted when/if it is safe to do so, in the opinion of the investigator. It is recommended that patients who experience a systemic hypersensitivity reaction be treated per the local standard of care. In the case of generalized urticaria or anaphylaxis, additional blood samples might be collected per investigator's judgement to diagnose and treat the event at local hospital.

If study drug is permanently discontinued, the patient will receive another glucose-lowering treatment, judged by the investigator to be appropriate based on the patient's clinical status, and will continue in the trial to collect all planned efficacy and safety measurements (see Sections 7.7.1 and 8.1.1).

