6.2. Site Level Unblinding

To preserve the blinding of the study, a minimum number of Lilly personnel will see the randomization table and treatment assignments before the study is complete. The treatment assignments will be blinded to patients and investigators until the end of the study.

Emergency un-blinding for AEs may be performed through the interactive web response system (IWRS). This option may be used ONLY if the patient's well-being requires knowledge of the patient's treatment assignment. All calls/ website visits resulting in an un-blinding event are recorded and reported by the IWRS.

The investigator should make every effort to contact the Lilly clinical research physician (CRP) prior to un-blinding a patient's treatment assignment. If a patient's treatment assignment is un-blinded, Lilly must be notified immediately by telephone.

If an investigator, site personnel performing assessments, or patient is un-blinded, the patient must be discontinued from the study. In cases where there are ethical reasons to have the patient remain in the study, the investigator must obtain specific approval from a Lilly CRP for the patient to continue in the study.

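### Protocol 7.3 and SAP 6.2 remove an unblinded patient from the study by default, while Protocol 8.1.1 stops study drug for the same event and keeps patients who stop drug in follow-up

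*Protocol*

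**What the plan says.** Protocol 7.3 (Blinding): "If an investigator, site personnel performing assessments, or patient is unblinded, the patient must be discontinued from the study". The next sentence allows an exception where there are ethical reasons to stay and the sponsor's clinical research physician gives specific approval. SAP 6.2 carries the same rule, "If an investigator, site personnel performing assessments, or patient is un-blinded, the patient must be discontinued from the study", with the same exception.

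Protocol 8.1.1 (Permanent Discontinuation from Study Treatment) opens a list with "patients will be discontinued from the investigational product in the following circumstances". One item is "If an investigator, site personnel performing assessments, or patient is unblinded". After the list, it says that patients who stop study drug permanently receive another glucose-lowering intervention and "will continue participating in the trial according to the protocol to collect all planned efficacy and safety measurements".

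Protocol 5.1 gives the same general rule without naming unblinding: "Patients who permanently discontinue study drug prior to the Safety Follow-Up Period will also be required to continue in the trial".

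Protocol 8.2 (Discontinuation from the Study) asks sites to make every attempt to keep patients in the trial. It names type 1 diabetes, pregnancy and enrolment in another study as situations that may warrant leaving, and it allows exit by sponsor, investigator or patient decision. Unblinding is not named there.

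**The concern.** The same trigger, in nearly the same words, leads by default to leaving the study in one section and to staying in it in another. Emergency unblinding is provided for adverse events, so the situation is foreseeable. For two events of special interest the Protocol wants follow-up to continue after drug stops. For pancreatitis, "the patient must discontinue therapy with investigational product, but will still continue in the study on another glucose-lowering regimen"; after permanent discontinuation for hypersensitivity, the patient "will continue in the trial to collect all planned efficacy and safety measurements". A site that breaks the blind to manage either event must decide which section governs.

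At stake is how uniformly post-unblinding data are collected. If sites follow 7.3, observation after the early termination (ET) visit and Visit 801 is lost. If they follow 8.1.1, it is kept. SAP 5.10 and the uncensored safety summaries are the analyses that would use those data.

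**Working it through.** **1. The rules side by side**

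| Source | Names unblinding? | Study drug | Study participation |
|---|---|---|---|
| Protocol 7.3 | Yes | Not stated | Must leave; staying needs ethical reasons and sponsor approval |
| SAP 6.2 | Yes | Not stated | Same as 7.3 |
| Protocol 8.1.1 | Yes | Stop | Patients who stop drug stay for all planned measurements |
| Protocol 5.1 | No | Already stopped | Must stay |
| Protocol 8.2 | No | Stops before exit | May leave for listed reasons or by decision |

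Listing unblinding in 8.1.1 is compatible with 7.3, because 8.2 stops drug before a patient leaves. The incompatible part is the continuation sentence that follows the list. Pregnancy and type 1 diabetes appear in both 8.1.1 and 8.2, so a site can see that they may end participation. Unblinding has no matching entry in 8.2.

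**2. Which analyses depend on the rule**

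- Primary and key secondary ITT analyses: no. Protocol 10.3.1 and SAP 5.2 censor efficacy data from premature treatment discontinuation onwards, and drug stops under either rule.
- Per-Protocol population: no. It requires completing treatment on study drug.
- SAP 5.10: yes. It uses the observed Week 28 value if the patient stays and a jump-to-reference (J2R) imputation if the patient leaves.
- Safety in general: yes. SAP 5.2 does not censor it, and the safety objective runs through 32 weeks.
- Hypoglycemia (SAP 5.11.2) and patient-reported outcomes (SAP 5.13): no. Both already leave out data after discontinuation.
- End-of-treatment laboratory tests and ECG: collected at ET, though earlier than Week 28.
- Disposition counts: yes.
- Completers: yes under Protocol Table GBGO.6, which refers to leaving the study; no under SAP Table 5.1, which refers to stopping treatment.

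**3. Size per patient in SAP 5.10**

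Inputs from Protocol 10.1: difference 0.5, SD 1.2, two-sided alpha 0.05, power 90%, dropout 15%. The stated sample size reproduces: the formula gives 122 per group against 123 stated, power at 123 is 90.4%, and 123 / 0.85 = 144.7, rounded up to 145 per group.

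Planning standard error = 1.2 × √(2/145) = 0.141.

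Shift in the treatment difference from one patient = gap / 145, where the gap is between the observed and the J2R-imputed HbA1c. The documents give no gap, so a range is assumed:

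| Assumed gap | Shift | Fraction of standard error |
|---|---|---|
| 0.5 | 0.5/145 = 0.0034 | 0.02 |
| 1.0 | 1.0/145 = 0.0069 | 0.05 |
| 2.0 | 2.0/145 = 0.0138 | 0.10 |

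A shift of 0.1 standard error needs 0.0141 × 145 = about 2 patients in one arm, each with a 1.0-point gap in the same direction. The direction is not fixed, because patients off drug in both arms receive another glucose-lowering intervention.

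**4. Contact lost per patient**

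A patient leaving at week t has Visit 801 at about t + 4 instead of week 32, so contact ends 32 − (t + 4) = 28 − t weeks early.

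| Leaves at | Scheduled visits lost | Contact ends early by |
|---|---|---|
| Week 4 | 11 (6 office, 5 telephone; Visits 7–17) | 24 weeks |
| Week 12 | 5 (3 office, 2 telephone; Visits 13–17) | 16 weeks |
| Week 24 | 1 (office; Visit 17) | 4 weeks |

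The existing adverse event is still followed to resolution or stabilisation (Protocol 9.2). After study exit, investigators need not actively look for new ones (Protocol 9.2.1).

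**The case against.** The strongest reply is that the sections can be reconciled. The 8.1.1 continuation sentence is tied to the protocol as a whole, and 7.3 is part of the protocol. Pregnancy and type 1 diabetes sit in the same list, so the sentence already gives way to study-exit rules and is not absolute. Section 8.2 also allows exit by sponsor or investigator decision, and 7.3 has its own route to stay.

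Part of this stands. A reader might infer that 8.1.1 forbids exit in every case, or that 5.1 itself deals with unblinding; neither is so. But the 8.2 provision only permits exit, whereas 7.3 requires it. The 7.3 exception makes staying something to be approved, whereas 8.1.1 makes it the rule. Nothing tells the site that 7.3 takes precedence.

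A reader might also see a direct contradiction with the pancreatitis and hypersensitivity sections. Neither mentions unblinding, so a conflict arises only when the event and a broken blind coincide, and the 7.3 exception might then be used.

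Finally, consistency could equally be restored by exempting 7.3 cases in 8.1.1 and 5.1. That is true, and it would avoid having unblinded staff collect data. It would also keep a loss of data that 8.2 sets out to minimise.

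**Conclusion.** The conflict is in current operative text and holds. It is minor.

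A reader might infer that the primary result is biased or loses power. The documents do not support that: censoring at drug discontinuation removes the same efficacy data under either rule. This assumes that values from the ET visit, where drug is stopped, count as falling at or after the censoring point.

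A reader might also take the 11 lost visits as a large safety loss. They overstate it, because the hypoglycemia and patient-reported analyses would not use those contacts and ET supplies the laboratory tests and ECG. The real loss is detection of new adverse events and later vital signs.

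What remains is 0.02 to 0.10 of a standard error per patient in SAP 5.10 (on the assumed gaps), some later safety observation, disposition counts, and Completers membership under the Protocol's definition only. The documents give neither an unblinding rate nor a split by cause, so the total cannot be computed, and it cannot be said how many unblindings would be for adverse events. The total is expected to be small.

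**What to change.** Amend Protocol 7.3 and SAP 6.2 along these lines: after unblinding of the investigator, site staff performing assessments, or the patient, study drug is permanently discontinued under 8.1.1, and the patient stays for all planned visits through Week 28 and Visit 801 unless a reason in 8.2 for leaving applies. Remove the default exit and the approval needed to stay. Flag these patients and the unblinding date in the listings.

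The cost is one wording change in each document and one listing flag; the visits are already scheduled. The downside is that some judgements of adverse-event relatedness, and some SAP 5.10 values, will be collected unblinded. The flag identifies them.

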7.4. Dosage Modification

No adjustment in study drug doses will be allowed. Further details about dose administration during the study are described in Section 7.2.1.

Dosing of required concomitant metformin and/or acarbose is discussed in Section 7.7.1.

7.5. Preparation/Handling/Storage/Accountability

The study site must store the SUP cartons in a locked and secure environment. The SUPs must be refrigerated (not frozen) at 2°C to 8°C until use. Dry ice should not be used for cooling. Patients will be provided with cartons containing 4 dulaglutide or placebo SUPs at office visits per the Schedule of Activities (Section 2). They will receive insulated bags with cooling gel packs for use in transporting the SUP carton from the site to home. Prior to self-injection, 1 SUP should be removed from the carton and allowed to sit at room temperature for about 30 minutes before self-injection. Investigational product will be labeled according to the China's regulatory requirements.

Patients will also be provided with a commercially available PG meter and test strips to use during the study. Sufficient study drug material and glucose testing supplies will be dispensed, as needed, at each visit.

Study site personnel must regularly assess whether the patient is correctly administering the assigned study drug and storing the study drug according to the provided instructions.

7.6. Treatment Compliance

The assessment of treatment compliance in this study will include assessment of administration of the study drugs (dulaglutide or placebo), the use of the TTT algorithm, administration of insulin glargine doses, and frequency of protocol deviations related to any glucose-lowering medications.

The assessment of treatment compliance with study drug will be determined by the following:

- Information about the administration of once weekly study drug injections will be entered into the patient diary by the patient and reviewed by the site personnel at each study visit; this information will be collected in the eCRF;
- Study drugs accountability will be checked according to the Schedule of Activities (Section 2). For that purpose, patients will be instructed to return the study drug carton at the next visit. They will also be instructed to return any unused study drug at the next study visit;
- Treatment compliance for once weekly study drug is defined as taking at least 75% of the required injections of study drug,
 - Between Visit 3 (randomization) and Visit 6 (Week 4), and
 - Since the previous visit, assessed at Visits 10 (Week 8), 12 (Week 12), 14 (Week 18), 16 (Week 24) and 17 (Week 28)

Compliance is assessed by site personnel; this information will be entered in the eCRF.

Compliance with the TTT algorithm will be determined by the following:

- The study site will review and document patients' use of the insulin glargine TTT algorithm for appropriate number of assessments, appropriate assessment of the insulin

dose, and subsequent dose adjustments at each visit from randomization to Visit 17. These data will be entered into the eCRF for the period prior to Visits 8 (Week 6), 10 (Week 8), and 12 (Week 12).

Other aspects of compliance with the study treatments will also be assessed at each visit, including the patient's adherence to the visit schedule, compliance with the concomitant metformin and/or acarbose requirements and other medication guidances (Section 7.7), completion of study diaries, results of SMBG, and any other parameters the investigator considers necessary. Patients considered to be poorly compliant with their medication and/or the study procedures (for example, missed visits or specific diagnostic tests) will receive additional training and instructions as required.

